# 5.4. Patient and Study Completion

This study plans to enroll a total of up to approximately 70 patients:

- Arm A (Phase II portion), Stage 1: 10 patients
- Arm A (Phase II portion), Stage 2: 19 patients
- Arm B (safety run-in): 12 to 18 patients (3 to 6 patients per regimen, out of which 6 patients must be treated at MTD or highest dose level)
- Arm B (Phase II portion), Stage 1: additional 4 patients (to reach the required 10 patients on the selected MTD or RP2D)
- Arm B (Phase II portion), Stage 2: 19 patients (to reach the total number of 29 patients on the selected combination dose)

In case none of the patients enrolled in Stage 1 of Arms A or B has a response evaluation of CR/iCR or PR/iPR, enrollment in the treatment arm can individually be stopped. All enrolled patients will be allowed to continue treatment until the end of treatment (EOT) criteria are met (see Sections 5.4.1 and 7.2.4); after the EOT Visit, they will proceed through the planned follow-up period (see Section 5.4.2) until end of study (EOS) (see Section 5.4.3).

#### **5.4.1.** End of Treatment Definition

EOT is defined as discontinuation of all study treatment administrations, i.e., IFX-1 alone or in combination with pembrolizumab treatment.

Discontinuation of study treatment does not represent withdrawal from the study.

An EOT Visit will be scheduled 30 days after last study treatment administration or before the patient starts on another antineoplastic therapy, whatever occurs earlier.

A patient, who discontinues study treatment administrations without progressive disease (PD)/confirmed PD (iCPD) will have tumor assessments at follow-up visits until PD/iCPD or start of subsequent antineoplastic therapy.

All patients will be followed for disease progression, survival status, and subsequent antineoplastic therapies as described in Section 5.4.2.

For details on treatment discontinuation criteria, see Section 7.2.4.

# 5.4.2. Follow-Up

Patients will be followed for survival and subsequent antineoplastic therapies every 3 months for 12 months after the EOT Visit. After the EOT Visit, tumor assessments will continue every 12 weeks until PD/iCPD or initiation of subsequent antineoplastic therapy for patients who discontinued study treatment for other reasons than progression. If required, information can be obtained by a phone call; a follow-up visit can be replaced by a phone call.

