- (8) FU every 3 months until 12 months after EOT Visit. All adverse events (AEs) with onset during treatment until EOT Visit will have to be followed until the outcome of the event is "recovering" (for chronic conditions) or until the end of study (EOS = last FU), and until all queries related to these AEs have been resolved. New related serious adverse events (SAEs) with onset during the follow up period (from the EOT Visit until the EOS) will have to be collected. FU visits may occur by telephone contact, if applicable.
- (9) 12-lead electrocardiogram (ECG): at screening, on C1D1 pre-dose and at H0+1 (±5 minutes), on C2D1 at H0+1 (±5 minutes), and at the EOT Visit
- (10) Hematology: red blood cells (RBC), white blood cells (WBC) with differential count, platelet count, hemoglobin, mean corpuscular volume (MCV) and hematocrit
- (11) Biochemistry: sodium, potassium, calcium, magnesium, alkaline phosphatase (ALP), total bilirubin, lactate dehydrogenase (LDH), aspartate aminotransferase (serum glutamic oxaloacetic transaminase (AST [SGOT]), alanine aminotransferase (serum glutamic pyruvic transaminase) (ALT [SGPT]), glucose, total proteins, albumin, urea, uric acid, creatinine, and C reactive protein (CRP).
- (12) Coagulation: activated partial thromboplastin time (aPTT), prothrombin time (PT).
- (13) Urine analysis: PH, glucose, leucocytes, proteins, blood.
- (14) Preferably Total T3, Free T4 should be analyzed, or other T3/T4 fractions (depending on local standards).
- (15) Pregnancy testing (WOCBP: women of childbearing potential only): During screening: serum beta-human chorionic gonadotropin test within 72 hours before first drug administration. During treatment period: urine pregnancy test. During FU urine pregnancy test on the first FU visit for Arm A, on the first FU visit and 120 days after the last dose of pembrolizumab for Arm B
- (16) Complement: C5a to be performed at pre-dose during treatment period. C3a to be performed only at C1D1 [pre-dose]
- (17) Antidrug antibodies (ADAs) against IFX-1 to be performed at pre-dose during treatment period.
- (18) Pharmacokinetics: To be performed at pre-dose during treatment period and in addition at the end of infusion H0+0.5h (-5/+10 minutes, but not before the end of IFX-1 administration) on Cycle 1 Days 1 and 22.

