# **5.4.3.** End of Study Definition

The EOS for the individual patient is defined as the date of the last contact of the 12 months follow-up period, date of death, date of consent withdrawal from study participation (see Section 5.4.4), or the date of last contact when patients are lost to follow-up (see Section 5.4.5).

The entire study will end when all patients have discontinued IFX-1 and IFX-1 + pembrolizumab treatment, AND all patients ended the study as described above.

The sponsor may prematurely terminate the study at any time earlier than planned for the following reasons:

- Unacceptable toxicity
- Administrative reasons

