#### 7.2.1. Treatment Administered

# 7.2.1.1. Monotherapy Arm A

IFX-1 monotherapy will be administered as a 30-minute (-5/+10 minutes) intravenous infusion. Because of the variability of infusion pumps from site to site, a window between -5 minutes and +10 minutes is allowed. Administrations will be given as follows (Figure 2):

- Cycle 1 Days 1, 4, 8, and 15: 800 mg IFX-1 (4 administrations).
- From Cycle 1 Day 22 on: 1600 mg IFX-1 Q2W until EOT (two administrations during Cycle 1 on Days 22 and 36 and 3 administrations per cycle on Days 1, 15, and 29 of Cycle 2 and all subsequent cycles).

Cycle 1 will comprise 7 weeks, whereas all following cycles will comprise 6 weeks of treatment.

Treatment will be continued until either disease progression is diagnosed, unacceptable toxicity occurred, or treatment has been administered for approximately 2 years.

[figure not shown]

Figure 2 Patient Calendar: Arm A (IFX-1 Monotherapy)

C: cycle; D: day; IC: informed consent; PD: progressive disease; Q2W: bi-weekly; Q6W: every 6 weeks; TA: tumor assessment.

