Response (CR/iCR/PR/iPR) duration	Duration of response will be analyzed for patients who reach at least PR/iPR at any time during the study using Kaplan-Meier methods. A responding patient who experiences any form of progression will be evaluated as a patient with event. The starting point is the first diagnosis of CR/iCR or PR/iPR. The time point of the event will be the diagnosis of progression according to RECIST. Responding patients without progression will be censored at their last tumor assessment showing response. Patients who never responded will be excluded from this analysis.
SD duration	Duration of SD will be analyzed using Kaplan-Meier methods. The starting point is the first study treatment administration. A patient who experiences any form of progression will be evaluated as a patient with event. The time point of the event will be the diagnosis of progression according to RECIST (PD) or iRECIST (iCPD). Patients without progression will be censored at their last tumor assessment showing response or any other best overall response except PD/iCPD.
PFS	PFS will be analyzed using Kaplan-Meier methods. A patient who experiences any form of progression or who

	dies of any cause will be evaluated as a patient with event.		
	The time point of the event will be the diagnosis of the		
	first progression according to RECIST/iRECIST or the		
	date of death. Patients without progression and still alive		
	will be censored at their last tumor assessment.		
OS	OS will be analyzed using Kaplan-Meier methods. Death		
	by any cause will be evaluated as event. Patients who are		
	still alive when they discontinue the study will be		
	censored at their last recorded date of being alive.		
Disease control rate	The number and percentage of patients with		
	SD/confirmed SD (iSD) per modified RECIST		
	v1.1/iRECIST or PR/iPR or CR/iCR will be displayed		
	per tumor assessment timepoint.		

Exploratory endpoints will be analyzed descriptively. Further details will be provided in the SAP.

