#### **Treatment Visits**

The Treatment Period will comprise mainly weekly visits until Cycle 1 Days 22 followed by biweekly visits until the EOT. Visits will have an accepted time window of between 1 and ±3 days as specified in the SoA (Table 1).

The following assessments and procedures will be performed during the treatment period:

- Re-check of all inclusion and exclusion criteria (Cycle 1 Day 1 pre-dose)
- Disease/response assessment (Day 1 of each cycle from Cycle 2 on until EOT Visit)
- QoL assessment (Cycle 1 Day 1 pre-dose-; Day 1 of each cycle from Cycle 2 on until EOT Visit)
- Documentation of concomitant disease and concomitant medication (Cycle 1 Days 1 [pre-dose], 4, 8, 15, 22, and 36; Days 1, 15, and 29 of each cycle from Cycle 2 on until EOT Visit)

- Check of re-dosing criteria pre-dose at Cycle 1 Days 4, 8, 15, 22, and 36, and Days 1, 15, and 29 of each cycle from Cycle 2 on until EOT Visit
- Study treatment administration by intravenous route as 30-minute (-5/+10 minutes) infusion:
  - Arm A (IFX-1 monotherapy):
    - o Cycle 1 Days 1, 4, 8, and 15: **800** mg IFX-1
    - O Cycle 1 Day 22 and Day 36, and from Cycle 2 onwards until EOT (Days 1, 15, 29 of each cycle): **1600** mg IFX-1 Q2W
  - Arm B combination regimen 1:
    - o Cycle 1 Days 1, 4, 8, and 15: **400** mg IFX-1 + 400 mg pembrolizumab on Day 8
    - Cycle 1 Day 22 and Day 36, and from Cycle 2 onwards until EOT (Days 1, 15, 29 of each cycle): 800 mg IFX-1 Q2W + 400 mg pembrolizumab Q6W (on Day 1 of each cycle)
  - Arm B combination Regimen 2:
    - o Cycle 1 Days 1, 4, 8, and 15: **600** mg IFX-1 + 400 mg pembrolizumab on Day 8
    - Cycle 1 Day 22 and Day 36, and from Cycle 2 onwards until EOT (Days 1, 15, 29 of each cycle): 1200 mg IFX-1 Q2W + 400 mg pembrolizumab Q6W (on Day 1 of each cycle)
  - Arm B combination regimen 3:
    - o Cycle 1 Days 1, 4, 8, and 15: **800** mg IFX-1 + 400 mg pembrolizumab on Day 8
    - Cycle 1 Day 22 and Day 36, and from Cycle 2 onwards until EOT (Days 1, 15, 29 of each cycle): 1600 mg IFX-1 Q2W + 400 mg pembrolizumab Q6W (on Day 1 of each cycle)
- Safety assessments:
  - Weight (Cycle 1 Days 1 [pre-dose], 4, 8, 15, 22, and 36; Days 1, 15, and 29 of each cycle from Cycle 2 on until EOT Visit)
  - Physical examination (Cycle 1 Days 1 [pre-dose], 4, 8, 15, 22 and 36; Days 1, 15, and 29 of each cycle from Cycle 2 on until EOT Visit)

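### Survival follow-up ends 12 months after each patient's own end of treatment, so OS censoring is informative from about 13 months and late Kaplan-Meier OS may be biased, in a direction the documents do not settle

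*Combined protocol and SAP*

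**What the plan says.** Section 5.4.2 sets the survival window: "Patients will be followed for survival and subsequent antineoplastic therapies every 3 months for 12 months after the EOT Visit". Footnote 8 of the Schedule of Assessments repeats it: "FU every 3 months until 12 months after EOT Visit". Section 5.4.3 makes that contact the individual's exit from the study: "The EOS for the individual patient is defined as the date of the last contact of the 12 months follow-up period" (or death, withdrawal or loss to follow-up). The same section keeps the study as a whole open until every patient has ended it.

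The clock starts from treatment discontinuation. Section 5.4.1: "An EOT Visit will be scheduled 30 days after last study treatment administration", or earlier if another antineoplastic therapy begins. Section 7.2.1.1 says what ends treatment: "Treatment will be continued until either disease progression is diagnosed, unacceptable toxicity occurred, or treatment has been administered for approximately 2 years". Section 7.2.1.2 is similar for Arm B.

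For the analysis, the OS row in Section 10.3.1 reads: "OS will be analyzed using Kaplan-Meier methods". Patients alive when they leave the study are "censored at their last recorded date of being alive". No common cut-off, truncation time or sensitivity analysis is given.

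Section 9.4 tells sites to follow everyone for survival and to collect death information to study end, without saying whether that means the individual's end of study or that of the entire study.

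**The concern.** Kaplan-Meier treats a censored patient as having the same future risk as those still under observation. Here the first surviving patients to be censored are those whose treatment failed first, and those who stay longest are those who were treated longest. This is not ordinary administrative censoring: an early-enrolled patient who progresses at the first scan leaves survival follow-up at about month 14 while the study is still running.

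OS is a secondary endpoint in both arms. The affected part of the curve, from 18 months on, is where a claim of durable benefit would be read. Deaths after the individual end of study are not collected, so a later analysis plan could model the problem but not recover the data.

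**Working it through.** **1. The plan's own figures.** No sample size, event count or landmark is given for OS. The only design calculation is Simon's two-stage design for ORR (Section 10.1: stop if 0 of 10 respond; reject the null if more than 3 of 29 respond). It reproduces:

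- Type I error: sum over x = 1 to 10 of P(X1 = x) × P(X2 > 3 - x), with X1 ~ Bin(10, 0.05) and X2 ~ Bin(19, 0.05), = 0.0468 (stated 4.7%).
- Power at 20%: 0.8011, so the type II error is 19.9% (as stated).
- Early termination: 0.95^10 = 59.9%. Expected N: 10 + 19 × 0.401 = 17.6 (stated about 18).

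The follow-up rule does not touch this decision.

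**2. When survival follow-up ends.** Scheduled end in months = (last dose day - 1 + 30) / 30.44 + 12. Cycle 1 lasts 7 weeks and later cycles 6, so the assessments on Day 1 of Cycles 2 and 3 fall on Days 50 and 92.

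| Patient | Last dose | End of survival follow-up |
|---|---|---|
| Dosed once | Day 1 | 30/30.44 + 12 = 13.0 months |
| PD at first assessment | Day 36 | 65/30.44 + 12 = 14.1 months |
| PD at second assessment | Day 78 | 107/30.44 + 12 = 15.5 months |
| Treated 2 years | month 24 | 24 + 1 + 12 = about 37 months |

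A new therapy can bring the EOT Visit, and so the end, somewhat earlier.

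**3. Effect on the OS estimate.** The documents give no PFS, post-progression survival or hazard shape for this population. The only anchor is Section 3.1, a median OS below 1 year in patients not responding to cemiplimab. All inputs below are therefore assumptions:

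- Time to progression is exponential with median 2 to 3 months. In some scenarios 10-20% of patients have long control, with median 18 months.
- Progression is detected at the next scheduled assessment; treatment is capped at 24 months.
- Post-progression survival has a median of 6 to 14 months, with either a constant hazard or one that falls over time (gamma frailty with variance 0.5 to 2, or 15% of patients with no further deaths).
- OS is censored at last dose + 30 days + 12 months. Each scenario has 400,000 patients.

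Kaplan-Meier minus true OS, in percentage points:

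| Scenario | 12 mo | 18 mo | 24 mo | 30 mo |
|---|---|---|---|---|
| (a) Constant hazard, no long-control subgroup | 0 | +0.2 to +0.4 | +0.3 to +1.0 | 0 to +1.4 |
| (b) Constant hazard, 10-20% long control | 0 | +1.3 to +1.7 | +5.1 to +6.1 | +7.0 to +9.1 |
| (c) Falling hazard, no long-control subgroup | 0 | -0.6 to -1.1 | -2.0 to -4.3 | -3.4 to -6.4 |
| (d) Falling hazard, 20% long control | 0 | +0.5 to +0.7 | +1.9 to +2.2 | +2.8 to +2.9 |

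If OS is independent of time to end of treatment, there is no bias beyond simulation noise (at most 0.2 point). The median moved by at most 0.2 month in any scenario.

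**4. Against sampling error.** In 3,000 simulated arms of 29 patients for each of four scenarios, the standard deviation of the 24-month estimate under the plan was about 10 to 15 points. Expected patients at risk at 24 months in those scenarios were 0.3 to 3.3.

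**5. After the change.** All patients were followed to a common cut-off, assumed at 36 months after first patient in with 12 months of accrual. Kaplan-Meier then matched true OS within 0.1 point in all four scenarios run. Two examples at 24 months:

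| Scenario | True | Plan | Common cut-off | At risk of 29: plan, then common cut-off |
|---|---|---|---|---|
| 20% long control, constant hazard, post-progression median 6 months (true median OS 10.9) | 18.7% | 23.8% | 18.7% | 3.2, then 5.4 |
| No long control, falling hazard, post-progression median 8 months | 27.9% | 24.9% | 27.9% | 0.3, then 8.1 |

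**The case against.** A reader might infer that the OS curve beyond 13 months is simply biased upward. The documents do not support that. Upward bias needs early progressors who survive a year after end of treatment to have a higher later hazard than the patients who remain. The plan gives neither a hazard shape nor a long-control share, and scenario (c) shows the opposite sign. A set of scenarios that all contain a long-treated subgroup with better survival after stopping would build in the upward answer. A further inference, that one arm would gain more from the bias in the descriptive comparison, has no calculation behind it.

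The consequence is also limited. OS is secondary and descriptive, no 18-, 24- or 30-month landmark is planned, and inference rests on ORR. With a median OS below 1 year, the median lies before the affected region, and few patients remain at risk at 24 months. The expected study duration of 3 years (Synopsis) limits how many would have 30 months of follow-up under any rule. All of this stands.

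Two arguments stand only in part. Section 9.4 can be read as already requiring survival follow-up to the end of the entire study, but on that reading it conflicts with Sections 5.4.2 and 5.4.3. Section 10.3 defers analysis details to a SAP whose contents are not visible here, so a sensitivity analysis may be planned there; it could not supply deaths that were never collected. And although the bias is smaller than the noise, it is systematic and the confidence interval does not show it.

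**Conclusion.** The concern holds in a limited form. From about 13 months, OS censoring is a function of time to treatment failure, and the planned Kaplan-Meier analysis does not allow for it. That follows from the text alone.

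Size and direction rest on the assumptions above. With a long-control subgroup the bias is upward, about +1 to +2 points at 18 months and +2 to +6 at 24. This is the more likely direction if the drug works as designed for (a 20% response rate) and those responses last, which is itself an assumption. Without such a subgroup it is near zero, or about -2 to -4 points at 24 months if post-progression hazard falls. OS to 12 months is unaffected, the median is little affected, and the ORR decision is untouched. This is an inexpensive improvement to a secondary endpoint and does not threaten the trial's main conclusion. It should be made early, because survival data are lost as each patient exits.

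**What to change.** In Sections 5.4.2 and 5.4.3, the Schedule of Assessments and Appendix 1:

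- Keep the 12-month limit for the other follow-up assessments.
- Continue survival status by telephone every 12 weeks for every patient until death, withdrawal of consent or one common cut-off, for example the last patient's end of study.
- In Section 10.3.1, censor patients still alive at that cut-off.
- Reconcile Section 9.4 with Sections 5.4.2 and 5.4.3 by stating which end of study is meant.

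This works whatever the direction of the bias. The cost is a protocol amendment, longer participation for surviving patients and some additional calls; Section 5.4.2 already lets a call replace a visit.

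If follow-up is not extended, report OS beyond about 12-13 months only with a stated caveat and a sensitivity analysis for informative censoring. Cutting the curve at 12 months would avoid the bias, but it is a trade-off: it discards all later survival data, including those of the long-treated patients.

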# **5.4.3.** End of Study Definition

The EOS for the individual patient is defined as the date of the last contact of the 12 months follow-up period, date of death, date of consent withdrawal from study participation (see Section 5.4.4), or the date of last contact when patients are lost to follow-up (see Section 5.4.5).

The entire study will end when all patients have discontinued IFX-1 and IFX-1 + pembrolizumab treatment, AND all patients ended the study as described above.

The sponsor may prematurely terminate the study at any time earlier than planned for the following reasons:

- Unacceptable toxicity
- Administrative reasons

# 5.4.4. Consent Withdrawal/Discontinuation of Study Participation

A patient may withdraw from the entire study at any time at his/her own request without the need to provide any reason(s).

If the patient withdraws from study participation, the sponsor may retain and continue to use any data collected before such a withdrawal of consent. Patients who wish to withdraw consent/discontinue the study while still on treatment should be encouraged by the investigator to perform the EOT Visit for their own safety before any further data collection for study purposes will be terminated. In such a case the EOS Visit information will be added to the EOT Visit information.

If a patient withdraws from the study, he/she may request destruction of any samples taken and not tested, and the investigator must document this in the site study records.

# 5.4.5. Lost to Follow-Up

A patient will be considered lost to follow-up if he or she repeatedly fails to return for scheduled visits and the study site is unable to make contact as described below.

The following actions must be taken if a patient fails to return to the study site for a required study visit:

- The site must attempt to contact the patient and reschedule the missed visit as soon as possible and counsel the patient on the importance of maintaining the assigned visit schedule and ascertain whether or not the patient wishes to and/or should continue in the study.
- Before a patient is deemed lost to follow-up, the investigator or designee must make every effort to regain contact with the patient (where possible, 3 telephone calls and, if necessary, a certified letter to the patient's last known mailing address or local equivalent methods). These contact attempts should be documented in the patient's medical record.
- Should the patient continue to be unreachable, he/she will be considered to have withdrawn from the study with a primary reason of lost to follow-up.

# 6. STUDY POPULATION

Prospective approval of protocol deviations to recruitment and enrollment criteria, also known as protocol waivers or exemptions, is not permitted.

# 6.1. Inclusion Criteria

#### **Type of Patients and Disease Characteristics**

- 1. At least 18 years of age on day of signing informed consent
- 2. Patients with biopsy-proven, histologically or cytologically confirmed (a.) locally advanced cSCC not amenable for curative treatment or (b.) metastatic cSCC. Patients must have been treated with all approved therapies for (a.) inoperable locally advanced cSCC contraindicated for radiation therapy or (b.) metastatic cSCC. All patients to be included must have progressed on PD-1- or PD-L1-inhibitory antibody therapy.
- a. Locally advanced cSCC not amenable for curative treatment:

Patients must have disease that is considered inoperable or medical contraindication to surgery or radiation or have not achieved disease control with these treatments.

Patients must have  $\geq 1$  measurable baseline lesion in which the longest diameter and the perpendicular diameter are both  $\geq 10$  mm on digital medical photography or that can be measured by CT/MRI as outlined in inclusion criterion 2b (metastatic cSCC).

Note: Non-measurable disease is defined as either uni-dimensionally measurable lesions, tumors with margins that are not clearly defined, or lesions with maximum perpendicular

diameters <10 mm. Patients without measurable disease at baseline are not eligible for the study.

- Surgery must be deemed contraindicated in the opinion of an expert in micrographics-controlled surgery (Moh's surgery, e.g., specifically trained dermatologic surgeon), a head and neck surgeon, or a plastic surgeon. A copy of the surgeon's consultation note from a clinical visit within 60 days of enrollment must be submitted. Acceptable contraindications in the surgeon's note include:
  - o cSCC that has recurred in the same location after ≥2 surgical procedures and curative resection is deemed unlikely
  - o cSCC with relevant local invasion that precludes complete resection
  - o cSCC in anatomically challenging locations for which surgery may result in severe disfigurement or dysfunction (e.g., removal of all or part of a facial structure, such as nose, ear, or eye; or requirement for limb amputation)
  - Other conditions deemed to be contraindicating for surgery must be discussed with the medical monitor before enrolling the patient
- Patients must be deemed as not appropriate for radiation therapy. Specifically, patients must meet ≥1 of the following criteria:
  - A patient previously received radiation therapy for cSCC, such that further radiation therapy would exceed the threshold of acceptable cumulative dose, per the radiation oncologist. A copy of the radiation oncologist's consultation note, from a clinical visit within 60 days of enrollment, must be submitted.
  - Judgment of radiation oncologist that such tumor is unlikely to respond to therapy. A copy of the radiation oncologist's consultation note, from a clinical visit within 60 days of enrollment, must be submitted.
  - O A clinic note from the investigator indicating that an individualized benefit-risk assessment was performed by a multidisciplinary team (consisting of, at minimum, a radiation oncologist AND EITHER a medical oncologist with expertise in cutaneous malignancies OR a dermato-oncologist, OR a head and neck surgeon) within 60 days prior to enrollment in the proposed study, and the radiation therapy was deemed to be contraindicated
- Acceptable contraindications to radiation therapy in the investigator's note for patients who have not received any prior radiation include:
  - o cSCC in anatomically challenging locations for which radiation therapy would be associated with unacceptable toxicity risk in the context of the patient's overall medical condition in the opinion of the multidisciplinary team (e.g., a neck tumor

for which radiation therapy would result in potential need for a percutaneous gastrostomy tube). A copy of the investigator's consultation note documenting the multidisciplinary assessment must be submitted.

- Other conditions deemed to be contraindicating for radiation therapy must be discussed with the medical monitor before enrolling the patient.
- The diagnosis of cSCC must be confirmed in all patients with locally advanced cSCC by histopathological examination of archived or newly obtained tumor material (biopsy at screening) to be performed centrally by a sponsor-appointed cutaneous histopathologist. Treatment with the investigational drug must not commence prior to confirmation of the diagnosis. If archived tumor material is not available requiring a new biopsy for the confirmation of the diagnosis, it should be considered to obtain the mandatory biomarker biopsy at baseline (inclusion criterion 5) at the same time in order to avoid having to perform a second biopsy prior to the initiation of treatment. If the biopsies to confirm the diagnosis and to conduct the biomarker assessments are taken at the same time, it is important to obtain sufficient material to allow for the biomarker assessments (the equivalent of a 4 mm x 4 mm punch biopsy) in addition to the material required for the confirmation of the diagnosis. This can be achieved by either by taking a sufficiently large biopsy to be divided prior to fixation or by obtaining two biopsies.
- An investigator note which states that the natural history of the patient's advanced cSCC would likely be life-threatening within 3 years with currently available management options outside of a clinical study
- b. Metastatic cSCC treated with all approved therapies for metastatic disease:

Patients are required to have histologic confirmation of distant cSCC metastases (e.g. lung, liver, bone, or lymph node). This confirmation of the diagnosis can be provided by a local investigator note based on the pathology review conducted locally.

Patients must have  $\geq 1$  baseline measurable lesion  $\geq 10$  mm in maximal diameter (1.5 cm in short axis for lymph nodes) according to RECIST v1.1 criteria (Appendix 3; Eisenhauer et al., 2009).

Note: In the case of a patient with metastatic disease that does not meet target lesion criteria by RECIST v1.1 criteria (e.g., bone only lesions, perineural disease) and with externally visible cSCC target lesions, Appendix 3 may be used, in which bi-dimensional measurements are required (at baseline, perpendicular diameters must both be  $\geq 10$  mm), after communication with and approval from medical monitor. The patient would then be enrolled with the plan to follow externally visible disease as target lesion(s), and metastatic lesions that are not measurable by RECIST v1.1 criteria may be followed as non-target lesions.

Note: There is no limit to the number of prior treatment regimens.

3. Patients must have progressed on treatment with an anti-PD1/L1 monoclonal antibody (mAb) administered either as monotherapy, or in combination with other checkpoint

- inhibitors or other therapies. PD-1 treatment progression is defined by meeting all of the following criteria:
- a. Has received ≥2 doses of an anti-PD-1/L1 mAb that has been approved for treatment of cSCC or any solid tumor
- b. Has demonstrated PD/iCPD after PD-1/L1 inhibitor treatment as defined by RECIST v1.1/iRECIST. The initial evidence of disease progression is to be confirmed by a second assessment ≥4 weeks from the date of the first documented disease progression, unless there is rapid clinical progression.
- c. Disease progression has been documented within 12 weeks from the last dose of anti-PD-1/L1 mAb.
- 4. The PD-1-/PD-L1 infusion must have been the most recent treatment for locally advanced or metastatic cSCC.
- 5. In addition to providing the material for ensuring the diagnosis as stated in inclusion criterion 2a for patients with locally advanced cSCC, patients must consent to undergo the following biopsies (at each time point a punch biopsy of externally visible cSCC lesions or a biopsy of material from accessible metastases) for biomarker assessments:
- a. At baseline prior to the first administration of the investigational therapy and if possible, within 7 days prior to initiation of study treatment administration (mandatory for all patients)
- b. For Stage 2 patients only: on Cycle 2 Day 1 (±3 days) (mandatory)
- c. For Stage 2 patients only: at the time of CR/iCR/PR/iPR (optional, to be conducted only if the investigator considers this biopsy as clinically possible and potentially informative)
- d. For Stage 2 patients only: At the time of tumor progression (optional, to be conducted only if the investigator considers this biopsy as clinically possible and potentially informative).

For all biopsies intended to analyze biomarkers, which needs to be the equivalent of a 4 mm x 4 mm punch biopsy. If biopsies for biomarkers are not feasible due to the complete absence of any suitable cutaneous or metastatic lesions, then this is not an exclusion criterion. However, this needs to be documented and confirmed by the investigator.

The biopsied lesion is not considered a target lesion.

- 6. Patients must have the following minimum washout before first study treatment administration from previous treatments:
- a. ≥4 weeks for mAbs, systemic cytotoxic anticancer therapy, treatment with other anticancer investigational agents
- b.  $\geq 3$  weeks for local radiation therapy
  - Note: Patients must have recovered from all radiation-related toxicities, not require corticosteroids, and not have had radiation pneumonitis. A 1-week washout is permitted for palliative radiation (≤2 weeks of radiotherapy) to non-central nervous system disease.
- 7. Eastern Cooperative Oncology Group performance status (ECOG PS) status of  $\leq 1$

